6.1 Study Agent(s) and Control Description

Study drug will consist of either one 2.0 mg dose of estradiol (obtained from Estrace® Tablets, 2.0 mg estradiol tablets, USP, Warner Chilcott [now Allergan, as Warner Chilcott was acquired by Allergan]) orally or look-alike placebo capsules. The IND number is 135357; this study has received an IND Exemption from the FDA given that our use of Estrace has met all 5 IND regulations set forth by the FDA (please see FDA letter included in the IRB application for details).

6.1.1 Acquisition

UTHealth Houston Investigational Pharmacy will dispense study medication in patient-specific kits. The research assistant assigned to this study will pick up the medication from the pharmacy with the study psychiatrist or nurse, will account for all study medication received. Any damaged or unusable study pills in a given shipment (active drug or placebo) will be documented in the study files. Study medication will be provided to the participants only by approved study clinicians who will review the medication prescription, instructions and answer any questions with the participant. The investigator will notify the pharmacy of any damaged or unusable study medication received.

6.1.2 Formulation, Appearance, Packaging, and Labeling

The Estradiol 2mg tablets and Placebo tablets will be prepared by a compounding pharmacy at both sites so the active and placebo pills are indistinguishable from one another in terms of appearance of the capsules. This will permit the appropriate concealment of the intervention from participants and study personnel alike, thereby enabling the double-blind. The capsules will be placed into a sealed plastic container and labeled clearly with the contents (drug, strength, quantity).

At the time of dispense, five capsules will be placed into an Amber vial with a child-resistant, tightly sealing screw-cap. The vial will be labeled as follows:

Caution: New Drug Limited by Federal (United States) Law to Investigational Use Only	UTHealth Houston -Investigational Pharm 

 
 
RX # XXXXXXXXX
 
Pt#: #####
 
 
 
Date: _____
 
Dr. _____
 
 
PATIENT NAME
 
TAKE ONE CAPSULE BY MOUTH ONCE AS INSTRUCTED
 
ESTRADIOL 2MG OR PLACEBO CAPSULES
 
 
Quantity: 5 Capsules
 
Refills: 0
 
 
Do Not Use After: MM/DD/YYYY PROTOCOL: HSC-MS-23-0497
	
---	--	--

6.1.3 Product Storage and Stability

Medication will be managed and stored in a double-locked medication closet at UTHealth Houston's Investigational Pharmacy. Study medication will be stored at ambient temperature. Temperature is monitored in the Investigational pharmacy daily. It remains at ambient temperature at the study site.

6.1.4 Preparation

The study drug is prepared and dispensed from UTHealth Houston's BBSB Pharmacy.

6.1.5 Dosing and Administration

A single dose of estradiol 2mg or placebo will be taken at home by the study participant 5-6 hours before each of 5 PE treatment sessions (sessions 2 to 6).

The study medication, 5 pills, will be given to the participant to take home after the first PE session by an approved study clinician (MD or NP) who will confirm the labelling and review the instructions with the participant. The subject will be instructed and reminded through a text or phone call to take the medication 5 hours before the time of each of their next 5 therapy sessions.

6.1.6 Route of Administration

The study medication will be taken orally.

6.1.7 Duration of Therapy

Subjects will take one pill 5-6 hours before each PE session 2-6, which will take place over the course of approx. 3 weeks. Typically, a minimum of 8-12 PE sessions are required for the treatment of PTSD. In our study design, we aim to examine the effectiveness of only 6 PE sessions that would be strengthened by the administration of estradiol. The interaction between exposure/extinction learning that occurs while estradiol is elevated (due to the pill) during 5 PE sessions is predicted to be sufficient to induce a significant reduction in PTSD symptoms in the active drug group compared to placebo.

Primary analyses will be based on a modified intent to treat sample including all participants who took at least one dose of the study medication.

6.1.8 Tracking of Dose

Medication records will be completed on a regular basis with the following information: date administered, amount administered and to which subjects, product remaining, product damaged/destroyed and date of damage/destruction, product returned and date of return, etc. A standard form will be utilized to document this information throughout the study period.

6.2 Study Agent Accountability Procedures

The Pharmacy will destroy remaining study medication, after the study research assistant, under the direction of the study nurse and/or physician, returns it to them from this site.

At the completion of the study, there will be a final reconciliation of drug dispensed, shipped, consumed, drug remaining. This reconciliation will be logged on the drug reconciliation form, signed and dated. Any discrepancies noted will be investigated, resolved, and documented prior to return or destruction of unused study drug. Drug destroyed on site will be documented in the study files.

7 Study Procedures and Schedule

The screening/baseline assessment must be completed within 4 weeks of the first experimental days. If more than 4 weeks have passed since the screening/baseline assessment, the study PI/clinician will advise if participant will be rescreened during a separate visit and/or the CAPS will be repeated at Experimental Day 1.

The 2-day experimental visits must occur on 2 consecutive days. All study treatment visits can occur within a window of 7 +/- 5 days from the previous visit.

Randomization to study medication will occur after the participant has come for Visit 3, and the participant will receive the medication and instructions for its use at visit 4 (the first PE session) so they can initiate medication at home 5 hours prior to visit 5 (the second PE session)

In order to have the study intervention and assessments be as complete as possible, any visit, with the exception of the pre- and post-experimental days, may be conducted remotely via Webex if needed at the discretion of the research team, such as in the circumstance of weather or a possible participant COVID-19 exposure. Webex will only be utilized if the research team has determined that the participant will be able to tolerate remote exposures safely.

7.1 Study Procedures/Evaluations

7.1.1 Screening/Baseline Phase

Subjects will complete a pre-screening survey on REDCap. The link to the initial REDCap survey will be included in our advertisements and potential participants will be screened out if they meet for any exclusion criteria. Once participants get through this survey, they will be contacted by a research coordinator to schedule the initial phone screen. An initial phone contact will be arranged with the study coordinator, or study team member, at UTHealth Houston based off of the initial pre-screening survey. During the initial contact, entry criteria will be reviewed and the study procedures will be outlined. Female subjects will be asked regarding their use of oral contraceptives as well as initial approved phone screening questions. Those women using oral contraceptives will be asked what kind to initially check if they are using 1st, 2nd, 3rd, or 4th generation, monophasic or biphasic oral contraceptives containing up to 35mcg of ethinyl estradiol as part of the phone screen (to be confirmed by the in-person screening clinician). For candidates who are interested in participating and appear to be potentially appropriate for enrollment, an onsite visit at UTHealth Houston for formal consenting (or consenting will be completed online via Redcap), and in person psychiatric assessment with an IRB approved study clinical evaluator will be arranged.

All participants will meet with a study clinician for consent (or complete consent online via Redcap) prior to the baseline in person screening evaluation and baseline assessments, consisting of a diagnostic interview and completion of the battery of self-report measures. The study clinical rater will describe the study in detail (i.e., the nature of the treatments and random assignment, duration of the treatment, fMRI component, payments for assessments, measurements collected, and follow-up procedures) and answer any questions. After signing the consent form, the participant will complete the clinician rated assessments and eligible participants will complete the self-report forms.

Participants who are deemed ineligible after baseline screening will be offered assistance with clinical referrals, as clinically appropriate. Individuals who have consented and are found ineligible after baseline screening, will have all identifiers related to their clinical screening maintained, unless the participant requests for such identifiers to be destroyed.

The initial evaluation will be conducted by a masters or doctorate-level clinician (or Independent Evaluator-IE) who is trained in psychiatric assessment. All study staff with the exception of the research pharmacy will be blind to medication treatment assignment. During the evaluation, the clinician or IE will interview the participant to assess current and lifetime disorders that meet exclusion criteria using the MINI, and to determine whether the participant meets the cutoff score using the CAPS-5 Past Month version. All efforts will be made to have the same independent evaluator assess the same patient throughout the course of the study when possible. Audio consent will be obtained to have all assessments audiotaped for reliability purposes.

If a participant does not meet PTSD/subPTSD inclusion criteria, the clinician or IE may offer to repeat the CAPS-5 Past Month assessment one week or more following the original baseline assessment visit. This will be offered at the clinician's discretion for participants whose scores are close to the cutoff score because symptoms may vary with time and/or changed circumstances. Participants will not be told the specific reason

for repeating the CAPS, but rather that further assessment is needed to determine eligibility. All baseline assessment measures must still be completed within 4 weeks of the initial experimental days.

Participants will also complete a pregnancy test before each scan to ensure safety of fMRI scanning and will be scheduled to complete the first (of a total of two) fMRI paradigm (see below) and the treatment sessions.

7.1.2 Experimental, Treatment, and Follow-up Days

Experimental Procedure: Fear conditioning and extinction paradigm

To assess the effects of the combined E2 and PE on the neurobiology of fear regulation, all participants will undergo our 2 day-fear conditioning and extinction paradigm before the commencement of PE and after the completion of the 6 PE sessions with double blind E2 or pill placebo. Psychophysiological experiments will be performed either in an experimental room or in the scanner.

Prior to the conditionability procedure, the subject will be reminded that a mild electric unconditioned stimulus (US) will be used and that if necessary she will be free to terminate the experiment at any time. Stimulating and recording electrodes will be attached. The stimulating electrodes will be attached to only one foot. Prior to setting the US level, the experimenter will give the following instructions: "For this experiment, you will set your own level of electric stimulation. You should choose a level that is highly annoying but not painful. I will start the stimulation at a very low level and gradually increase the level until you say 'stop'. The level that you set will then be used throughout the remainder of the experiment." After the US level is established, the experiment will begin.

Prior to the initiation of the experiment, subjects will view pictures of two rooms presented on a monitor, both of which differ in color and content (e.g., an office and a conference room). The conditioned stimuli (CSs) will be three different cues in the room (e.g. a light that differs in color: yellow, blue and red). Two of these lights will be followed by the US at a partial reinforcement rate of 62.5% (CS+s). The third CS will never be followed by the US. The CS+s, CS- and the US will only be presented in one context (conditioning context; CX+). The other context will be used for extinction training (CX-). Neither CS+ presented in the context of the CX-, nor a CS- presented in either context, will ever be paired with the US. The experiment will be composed of five sequential phases. The initial Habituation phase will consist of 4 presentations of the to-be CS+ (i.e. blue), 4 presentations of the other to-be-CS+ (i.e. red) and 4 presentations of the to-be-CS- (i.e. yellow) in pseudo-random order (there will be no more than two consecutive presentations of the same type), all in the context of the CX+. Each CS will last 6 sec. The inter-trial-interval will be 15 + 3 sec., determined at random.

Immediately after will be the Conditioning phase, which will consist of presentations of each stimulus type in pseudo-random order, again all in the context of the CX+. At the offset of 5 out of 8 trials CS+ (but not CS-); a 500-msec. electrical current US will be administered. There will be a total of 8 CS+ (blue), 8 CS+ (red) and 16 CS- (yellow) trials during the conditioning phase. After a rest period, the Extinction phase will begin. During extinction, the CS- and only one of the CS+s (Extinguished CS+, CS+E) will be presented in the context of the CX-, and no US will be delivered. There will be a total of 16 CS+E trials and 16 CS-trials.

One day after extinction training, the subject will return for the Extinction Recall phase (extinction memory test). During this test, the CS+, CS-, and the Unextinguished CS+ (CS+U) will be presented. There will be 8 CS+E, 8 CS+U, and 16 CS- trials presented during this phase in the extinction context (CX-). Following a brief rest period, the Renewal phase will be administered. The Renewal phase will be identical to the Extinction Recall phase except that all stimuli will be presented in the conditioning context (CX+). No shocks will be delivered during either phase during the retention test.

Treatment with Prolonged Exposure combined with E2 or placebo:

To test the hypothesis that E2 will augment the efficacy of PE in reducing PTSD symptoms, we propose to conduct a double-blind placebo controlled study in which we will administer E2 or placebo to women with significant PTSD symptoms who undergo PE. 2mg of synthetic estradiol (Estrace) will be administered 5 hours prior to each of the 5 PE therapy sessions in which imaginal exposure will be administered (PE sessions 2 to 6). An automatic reminder will be sent to the participant when medication has to be taken in order to increase compliance. After the first introductory PE session, 5 imaginal exposure sessions will occur, such that there will be 2 sessions per week conducted for a total of 6 sessions over 3 weeks (more details in

the next section). The timing of the E2 administration was selected using our preliminary data that was based on the pharmacokinetics obtained from a recent publication. These data show that peak estrogen levels are achieved approximately 6 hours after ingestion (therapy session would be ending or about to end). This timing would allow for maximum estrogen levels to be present to strengthen the consolidation of the safety memory acquired during the therapy.

Therapy Sessions and Assessment During Treatment:

Session 1. This session provides an overview of the PE treatment and a general rationale for exposure, along with the proposed mechanism of action of estrogen on the exposure process. The therapist (same for all sessions) gathers information about the patient's symptoms, details of the trauma, history of previous trauma, and functioning, and provides an explanation of PTSD and discusses common reactions to trauma and the rationale for treatment. In addition, the therapist will construct an in vivo hierarchy with the patient, which is why this session is extended to 120 minutes. The study medication, 5 pills, will be given to the participant to take home after the first PE session by an approved study clinician (MD or NP) who will confirm the labelling and review the instructions with the participant.

Sessions 2-5. These sessions are 60 minutes long and consist of imaginal exposure. Specifically, the patient is instructed to imagine the trauma and recount it aloud for about 25-30 minutes. In the following 15 minutes, the patient processes her reactions to revisiting the traumatic event by discussing related thoughts and feelings. The session ends with in vivo exposure homework to be completed that same day as the session.

Session 6. In this last session, imaginal exposure is conducted one last time for the same duration as previous sessions. The therapist and patient review treatment progress and discuss applications of treatment principles to daily life.

Participants will complete the PDS-5 and BDI-II at each session and the PTCI at baseline, Visit 5, 7, and 9. A non-invasive skin conductance monitor (purchased from Mindfield eSense Skin Response) will be used to measure skin conductance throughout the imaginal exposure sessions. Electrodes will be placed on the fingers of the participant and will be connected to an iPad to record the skin conductance throughout each PE session. This will not cause discomfort or any additional risk to the subject.

Post-treatment Assessment:

Lastly, an independent evaluator, blind to treatment assignment, will assess PTSD severity after therapy (Visit 12) (following same procedures as before therapy (Visit 1), and at 3 and 6 month follow-up visits) using the CAPS-5 Past Week version to assess whether changes in symptom severity are stable over time, and to detect any effects of the experimental manipulation on reduction of fear.

Follow-Up Assessments (3 and 6 months post-treatment):

These assessments will be identical to the post-treatment clinical and self-rated questionnaire assessments, and the 6-month follow-up will also include the CAPS-5 Past Month assessment. There is no additional experimental conditioning, fMRI or pregnancy test in follow up. In addition, participants will be asked to report any psychological, psychiatric and medical treatment they received since the last assessment. This information will be recorded on the Additional Treatment Inventory (ATI). Each follow up visit will include a clinical safety assessment for suicidality, and consider the potential need for clinical referrals, as above.

Participants who do not improve at least 30% from the pre-treatment to 3-month follow-up CAPS-5 Past Week score and who have a CAPS-5 Past Week score of 26 or greater at the 3-month follow-up assessment will be offered additional PE treatment at UTHealth Houston if they wish. Specifically, participants will have the option to receive up to 4 additional sessions of PE delivered for an hour a week (for a total number of 10 sessions of PE) immediately following the 3-month follow-up, consistent with prior study designs utilizing PE and to mimic real world clinical practice where patients receive a variable number of sessions of PE. The need for clinical referrals will be discussed and assessed with all participants by the study clinician regardless of endpoint improvement scores, and referrals made when indicated.

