In addition, any participants who have not improved at least 30% from their pre-treatment the 3-month follow-up CAPS-5 Past Week score and have a CAPS-5 Past Week score of 26 or greater at the 3-month follow-up will be offered additional treatment if they wish. Participants will then have the option to receive up to 4 additional sessions of PE delivered for an hour a week (for a total number of 10 sessions of PE) immediately following the 3-month follow-up visit. All participants will receive safety assessments throughout the study and at 3 and 6 month follow ups, and will be assisted with clinical referrals if desired and/or indicated.

Monitoring of Mental Status and Mood. Subjects' mental status will be closely monitored throughout the course of the study. As previously stated, it is not uncommon for treatment of trauma-related symptoms to be associated with temporary exacerbation in participants' symptoms of PTSD and depression. However, some participants may experience symptom exacerbations or psychiatric emergencies that require treatment beyond that provided by the study. In all cases, the client's mental status will be the utmost priority and immediate action will be taken to provide appropriate care. The intake evaluation for the study will include the Columbia-Suicide Severity Rating Scale to adequately assess suicide risk before study enrollment, and study therapists will routinely evaluate mood over the course of treatment, including the presence or absence of suicidal thoughts (using the BDI-II followed by clinical interview with a modified suicide check list at each

visit), and if any suicidal thoughts, plans or actions are present, these will be dealt with using the detailed plan outlined in Protection against Suicidality in the section immediately below.

Management of Suicide Risk

Several strategies will be implemented to assist in early identification and appropriate management of suicide risk. This protocol will utilize the Columbia Suicide Scale (C-SSRS) at screening and a suicide check list at each clinical and psychiatric assessment follow up visit to routinely assess suicidal ideation, impulses and behaviors. In addition, the BDI will be completed and reviewed by the study therapist who will be working closely with each participant.

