9.3 Analysis Datasets

The proposed experiments in this project are aimed to examine the effects of E2+PE on the extinction-induced SCR and neural responses at post-PE sessions relative to pre-PE. SCR will be recorded as a psychophysiological index of fear extinction and extinction recall. We will conduct standard fMRI analyses to examine information flow changes in the extinction network. These data will test hypothesis 1 stated above.

Another objective of the project is to examine the impact of E2 administration on PE efficacy at reducing PTSD symptom severity. Here, we will use all clinical data (CAPS) before and after treatment as well as 3, 6 months follow up data. These data will be used to test hypothesis 2 stated above.

The combined data sets will then be used to test hypothesis 3 above.

Primary analyses will be based on a modified intent to treat sample including all participants who took at least one dose of the study medication.

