9.4.6 Baseline Descriptive Statistics

We will perform descriptive statistics prior to testing our hypotheses. These statistics will include means (or frequencies and proportions for categorical variables), standard deviations, skewness and kurtosis, and odds-ratios. Variables with distributions violating assumptions of normality will be transformed. If this fails to improve the normality of the distribution, distribution-free statistics will be employed. This study has baseline, post-treatment, and two follow-up assessments, creating clustered data due to repeated measures. Thus, we will use established methods for such study designs to examine treatment differences, including the two most popular approaches for longitudinal data modeling: the generalized estimating equations (GEE) and linear mixed-effects model approach (LMM). We will apply these models for both the intent-to-treat and completer analyses. Inference based on GEE or LMM is valid provided that missing data are non-informative or "missingness" does not depend on the value of the unobserved outcome. Although missing data in many studies in mental health research are non-informative, we will perform sensitivity analyses to ensure that this is the case. In particular, we will entertain both parametric and semi-parametric models that assume some missingness mechanism and compare estimates obtained from such models with those from GEE and LMM. Such analyses will inform us whether the non-informative missingness assumption is violated and if so, to what extent. If the non-informative missingness assumption is deemed to be severely violated, we will report treatment effects using the methods that account for informative missingness.

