9.5 Sample Size

Pre to post treatment assessment using our experimental approach has not been previously conducted, and therefore it is challenging to calculate power to estimate potential sample or effect size comparing the pre to post time-points. The following sample size calculations pertain to the expected changes related the psychophysiological and neurobiological indices to be obtained. The sample size selected for this proposal is based on the detection of between-group significant differences at an alpha of .05 using data collected in our previous study of fear conditioning and extinction recall in controls and patients (PTSD) and using our preliminary fMRI data in women with high (HE) vs. low estradiol (LE) (Zeidan et al, 2011). We have calculated our power to detect between-group differences with a sample size of 25 subjects per group. Based on our previous experience with this population and this paradigm, we expect that (at each of the two time points) it is possible that we will have unusable data in approximately 20% of the subjects due to data of insufficient quality for at least one phase of the experiment. Reasons for this include poor SCR responses, head motion during scanning, or technical difficulties with SCR or fMRI. In addition, we anticipate dropout of ~20 % of patients after the initiation of the study. Thus out of the total of 80 patients, we expect to obtain a full data set (from all time points) from 50 patients. By using the effect size obtained from our previous study (see above), an alpha level of 0.05 and 50 patients, we will have 85% power to detect a significant between-group difference. Regarding the clinical measures, we do not have data to calculate power because of the novelty, but since it is a preliminary proof-of-concept aim, the results to be obtained will help inform future power analyses and calculations for this line of research.

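### Session PDS-5 and BDI-II scores have no stated role in handling missing CAPS, so the Hypothesis 2 comparison can be biased if dropout follows symptoms differently by arm

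*Combined protocol and SAP*

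**What the plan says.** - **In-treatment measures.** Section 7.1.2: "Participants will complete the PDS-5 and BDI-II at each session and the PTCI at baseline, Visit 5, 7, and 9". Table 2 in section 7.3 likewise lists PDS-5 and BDI-II at PE sessions, and no CAPS there. The Schematic of Study Design also places PDS-5 at Visits 1, 12, 13 and 14.
- **CAPS.** It is scheduled at Visit 1, Visit 12 and the two follow-ups. For Hypothesis 2, section 9.3 states: "we will use all clinical data (CAPS) before and after treatment as well as 3, 6 months follow up data".
- **Model.** Section 9.4.6 describes baseline, post-treatment and two follow-up assessments and names "the two most popular approaches for longitudinal data modeling: the generalized estimating equations (GEE) and linear mixed-effects model approach (LMM"). It lists no covariates or auxiliary variables. It ties validity to non-informative missingness, promises sensitivity models that assume some missingness mechanism, and would report informative-missingness methods if the assumption is severely violated. No mechanism, variable or threshold is given.
- **Dropout.** Section 9.5: "we anticipate dropout of ~20 % of patients after the initiation of the study". It is not split by arm, cause or time.
- **After discontinuation.** Sections 5.7.2 and 8.1 schedule a final evaluation for patients who require discontinuation, without naming instruments. Section 8.1 treats stopping treatment and stopping assessments as separate choices. Table 1 has no early-termination column.

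**The concern.** An LMM on CAPS alone is valid if dropout depends only on arm and the CAPS values already seen. Unweighted GEE needs more than that, a difference that 9.4.6 does not draw. For a woman who leaves during PE and is not assessed again, the only CAPS seen is the one from before treatment, so the model predicts her outcome from arm and baseline. Whatever happened to her during therapy is ignored, although it was recorded at each session she attended.

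Symptom change during PE is a plausible reason for leaving. Section 8.1 says that "it is not uncommon for treatment of trauma-related symptoms to be associated with temporary exacerbation". If leaving follows that course, and does so differently in the two arms, the E2 contrast on CAPS shifts. The session PDS-5 is the only repeated PTSD symptom measure between Visits 1 and 12, so it is the obvious way to make the missing-at-random assumption more credible. All analyses follow unblinding (section 9.4.9), so its role should be fixed beforehand.

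**Working it through.** **1. The plan's own figure.** Section 9.5 expects 50 full data sets from 80 patients, after about 20% unusable data and about 20% dropout.
- Sequential losses: 80 × 0.8 × 0.8 = 51.2.
- Additive losses: 80 × (1 − 0.40) = 48.

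Either agrees with 50. The figure concerns SCR and fMRI. The statement "we will have 85% power to detect a significant between-group difference" also concerns those endpoints and cannot be checked, because no effect size is printed. No CAPS power is given.

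**2. Numbers for CAPS.** If all the dropout fell before Visit 12, 80 × 0.20 = 16 women would be missing. That leaves 64 observed, about 32 per arm. Assuming a baseline–post correlation of 0.5, the standard error of the adjusted difference is √(2/32 × (1 − 0.5²)) = √0.0469 = 0.22 SD.

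**3. How bias arises.** Let a fraction π of one arm be missing, and let those women end e SD worse than arm and baseline CAPS predict. Residuals average zero over the whole arm, so completers sit at about −eπ/(1 − π). At π = 0.2 that is −0.25e. Leavers who are 0.52 SD worse than predicted shift that arm's mean by 0.25 × 0.52 = 0.13 SD. Equal shifts in both arms cancel; opposite shifts add.

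**4. Simulation.** 400,000 records, 20% dropout, and no post-baseline CAPS from leavers. These inputs are assumptions, not figures from the documents:
- correlations: baseline–post CAPS 0.3 to 0.5, last PDS-5–post CAPS 0.7 to 0.8, baseline CAPS–PDS-5 0.4 to 0.5;
- log-odds of dropout per SD: 0.5 to 1.5;
- true effect: 0 or 0.5 SD.

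The CAPS-only column conditions on arm and baseline CAPS. The other column also uses the last-session PDS-5, by arm. Bias is in SD of CAPS, and negative values favour E2.

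| Dropout rule | CAPS only | With PDS-5 |
|---|---|---|
| Same PDS-5 rule in both arms, null | 0.00 | within 0.01 |
| Same PDS-5 rule in both arms, true effect 0.5 | at most 0.04 attenuation | within 0.01 |
| Follows high PDS-5 in E2 arm only | −0.04 to −0.14 | within 0.01 |
| Follows high PDS-5 in placebo arm only | +0.04 to +0.13 | within 0.01 |
| High PDS-5 leave placebo, low leave E2 | +0.09 to +0.27 | within 0.01 |
| Follows unobserved CAPS, opposite by arm | 0.14 to 0.42 | 0.07 to 0.25 |

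In the last row, PDS-5 removes only about 30 to 50% of the bias. If the final evaluation obtains CAPS from half of the leavers, the CAPS-only bias falls by a little more than half. If it obtains CAPS from all of them, the bias is zero.

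**5. Trial-sized check.** This used 40 per arm, 21 to 24% dropout and a true effect of about 0.3 SD.
- Placebo leavers are non-improvers and E2 leavers are unrelated to symptoms: attenuation of 37 to 49%, that is 0.37 × 0.3 = 0.11 to 0.49 × 0.3 = 0.15 SD.
- Common rule: 8 to 12%, about 0.02 to 0.04 SD.
- Random dropout: no bias, and a standard error 4 to 8% smaller when PDS-5 is used.

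**The case against.** A reader might infer that everyone who leaves mid-treatment is represented by baseline CAPS alone. The documents do not support that. A final evaluation is scheduled, stopping treatment is distinct from stopping assessments, and nothing removes women who stop PE from Visits 12 to 14. Section 7 allows remote visits to keep assessments complete, and section 11 plans training in follow-up methods. The statement holds only for women who give no later CAPS.

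A reader might also infer that the plan specifies a missing-data model and excludes the session scores from it. It does not: 9.4.6 leaves the model open and promises informative-missingness analyses. The fair criticism is vagueness.

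Nor do the documents show that the E2 effect will be biased, or that attenuation of 37 to 49% is likely. The exacerbation in section 8.1 comes from PE, which both blinded arms receive, and is described as temporary. That points to a common dropout rule at least as much as to an arm-specific one, and a common rule gives little or no bias. The 20% dropout is not all mid-PE: some may fall before the first dose, outside the modified intent-to-treat set, and some after Visit 12.

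Finally, the near-complete repair in most rows of the table follows from letting dropout depend on the observed PDS-5.

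What still stands is that a relevant measure, already collected, has no stated role, and that the promised sensitivity analysis is not defined well enough to supply one.

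**Conclusion.** The concern holds as a conditional one. For women with no CAPS after baseline, the planned analysis makes no stated use of their session scores, and differential symptom-driven dropout could then bias the CAPS comparison in either direction. At the largest, about 0.27 SD, the bias exceeds the standard error of about 0.22 SD. With one selective arm it is 0.04 to 0.14 SD, and under a common rule between nil and about 0.04 SD. These sizes rest on the assumed correlations and dropout rules, on 20% missing at Visit 12, and on no CAPS recovered from leavers. The documents give no data on dropout by arm. CAPS is the secondary endpoint, and section 9.5 calls the clinical aim a preliminary proof of concept. This is a modest, inexpensive improvement.

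**What to change.** In section 9.4.6:
1. Prespecify a compact auxiliary set for missing Visit 12 to 14 CAPS. An example is Visit 1 PDS-5, the last observed session PDS-5 or its slope, and at most one BDI-II value, together with arm, baseline CAPS and the severity stratum. Entering all seven PDS-5 scores (Visit 1 and Visits 4 to 9) on top of the other terms would be too many for about 64 observed outcomes.
2. Use multiple imputation, or a joint mixed model of session PDS-5 and CAPS, and report the CAPS-only LMM alongside.
3. State that this removes bias only to the extent that dropout depends on the observed session scores, and define one MNAR sensitivity analysis.

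In sections 5.7.2 and 8.1, state whether the final evaluation includes CAPS Past Week.

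The auxiliary scores are already collected. The cost is SAP wording and a little programming, and the imputation model must stay small at about 32 observed per arm.
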